7. EFFICACY ANALYSES

7.1. General Considerations

Efficacy analyses will be conducted on the Extension Study population according to the parent study randomized treatment assignment. Stratified analyses will incorporate the randomization stratification factors. If the group of patients at any factor level from a randomization stratification factor (eg, patients with Baseline MBL volume ≥ 225 mL) comprises $< 10\%$ of the entire mITT population, this stratification factor (eg, Baseline MBL volume) will not be used for stratified analyses. In addition, if there are < 15 patients in 1 of the 4 strata (derived from the 2 stratification factors each with 2 levels), only stratification factor of Baseline MBL volume (< 225 versus ≥ 225 mL) will be used in the stratified analysis for more robust strata-adjusted estimation of treatment effect. The stratification category used at the time of randomization (in the Interactive Web Recognition Service [IWRS] system) will be used for all analyses rather than data recorded on the electronic case report form (eCRF) unless otherwise specified.

No formal treatment comparisons will be performed for this extension study. As there is no inferential statistics for this analysis, there is no need for multiplicity adjustment.

7.1.1. Analyses for Categorical Data

Qualitative variables will be summarized by frequency counts and percentages. Unless otherwise specified, the calculation of proportions will include the missing category. Therefore, counts of missing observations will be included in the denominator and presented as a separate category.

For efficacy endpoints evaluating proportions descriptive statistics (point estimates and corresponding 95% CIs) will be provided by treatment group and visit as appropriate.

7.1.2. Analyses for Continuous Data

Continuous variables will be summarized using descriptive statistics (eg, n, mean, median, SD, minimum, and maximum). For the analyses of change from Baseline, the mean at Baseline will be calculated for all patients with at least one post-Baseline value by treatment group. Additionally, the mean will also be calculated for each visit, including only the patients who are in the analysis who have data for that visit by treatment group.

For endpoints evaluating the change (absolute or percent change) from Baseline to Week 52, mean change as well as least squares (LS) means change and 95% CI will be summarized. LS means and 95% CI will be derived separately for each treatment group using a mixed model repeated measures approach with randomization stratification factors included as fixed effects. The Baseline value will be included as a covariate, and an unstructured variance-covariance matrix will be assumed. If the mixed model fails to converge, a first-order autoregressive variance-covariance matrix will be used. Calculation of the dependent variable (change from Baseline) for each patient at each visit will be calculated based on the visit windows specified in [Section 4.3.8](#). In addition, summary statistics (mean change or mean % change) will be graphically presented as appropriate.

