4. GENERAL CONSIDERATIONS FOR DATA ANALYSES AND HANDLING OF MISSING DATA

4.1. Data Presentation Conventions

All statistical analyses will be conducted using SAS[®] Version 9.2 or higher.

All confidence intervals (CIs) will be reported as two-sided unless otherwise stated.

Where appropriate, variables will be summarized descriptively by study visit. For the categorical variables, the count and proportions of each possible value will be tabulated by parent study treatment group. For continuous variables, the number of patients with non-missing values, mean, median, standard deviation (SD), minimum, and maximum values will be tabulated.

Unless otherwise specified, the following conventions will be applied to all analyses:

- Mean and median values will be formatted to one more decimal place than the measured value. Standard deviation values will be formatted to two more decimal places than the measured value. Minimum and maximum values will be presented to the same number of decimal places as the measured value. If the measured value is large (eg, > 100), fewer decimal places may be displayed.
- Percentages will be rounded to one decimal place;
- p-values will be rounded to four decimal places. p-values < 0.0001 will be presented as “< 0.0001” and p-values > 0.9999 will be presented as “> 0.9999”;
- 1 month = 30.4375 days. Month is calculated as (days/30.4375) rounded to one decimal place;
- 1 year = 365.25 days. Year is calculated as (days/365.25) rounded to one decimal place;
- Age will be calculated using the date of randomization. If only year of birth is collected, 1 July of the year of birth will be used to calculate age.
- 1 pound = 0.454 kg;
- 1 inch = 2.54 cm;
- Missing efficacy or safety data will not be imputed, unless otherwise specified;
- For laboratory results above or below sensitivity limits displayed as “<” or “>,” a quantification threshold, 0.0000000001, will be subtracted or added, respectively, to the threshold to derive a numeric result for analyses;
- For MBL volume reported as below the limit of quantification (for example, MBL below Quantification Level <5.0 mL or <2.5 mL), 0.0000000001 will be subtracted from the reported quantification threshold for the visit to derive a numeric result for analyses;
- For safety analyses, calculation of percentages will be calculated on the basis of the number of patients in the analysis population in each parent study treatment group;

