- For by-visit observed data analyses, calculation of percentages will be calculated on the basis of the number of patients with non-missing data as the denominator, unless otherwise specified;
- For other continuous endpoints, the summary statistics will include mean, SD, median, and range (minimum and maximum);
- For categorical endpoints, the summary statistics will include counts and percentages;
- Confidence intervals, when presented, will generally be constructed at the 95% level. For binomial variables, exact methods will be employed, unless otherwise specified.

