For revised activities, the proportion of patients who are responders (defined as meeting a meaningful change from Baseline in the revised activity score) at Week 52 will be analyzed similarly to that for the change in BPD Scale score for each treatment group. The proposed responder threshold is a 20-point increase. Details of the determination of the meaningful change in the Revised Activities Scale score can be found in the MVT-601-3001/3002 SAP Appendix 5.

Missing Items

For any scale analyses, if < 50% of the scale items are missing, the scale should be retained using the mean scale score of the items present. If ≥ 50% of the items are missing, no scale score should be calculated; the subscale score will be considered missing.

7.3.5. Change from Baseline to Week 52 in Uterine Volume and Uterine Fibroid Volume

For evaluating percent change from Baseline in uterine fibroid volume and uterine volume that are measured at Week 52, an analysis of covariance (ANCOVA) model will be used to calculate LS means and 95% CI, with randomization stratification factors and Baseline value as covariates. This model will be run separately for each treatment group.

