9.3.4. Bone Mineral Density

Corrected BMD data will be used for analysis as determined by the central radiology laboratory in the three prespecified anatomical locations: lumbar spine (L1–L4), total hip, and femoral neck.

BMD measured at Baseline, Week 12, Week 24, Week 36, and Week 52 visits will be summarized descriptively by parent study treatment group and each measured anatomical location for all patients in the Extension Safety population. Percentage changes from baseline along with 95% CIs of mean percentage changes also will be summarized by parent study treatment group and anatomical location. Mean percentage change from baseline with its corresponding 95% CI will be plotted by visit, parent study treatment group, and anatomical location.

A mixed-effects model with repeated measures will be used to assess BMD at 12, 24, 36, and 52 weeks. The model will be generated separately for each parent study treatment group and will have age at Baseline, visit, Baseline BMD value, stratification factors (geographic region and menstrual blood loss volume [as entered in the interactive web response system at the time of randomization]), race (African American versus Other), and BMI at Baseline as fixed effects using an unstructured variance-covariance matrix. Least square means on each anatomical location will be presented and plotted at each visit with associated 95% CIs. Categorical representation of percentage change from Baseline to 12, 24, 36, and 52 weeks of treatment will be presented by the number and proportion of patients who had BMD declines of $\leq 2\%$, $>2\%$ to 3% , $>3\%$ to 5% , $>5\%$ to 8% , and $>8\%$ by parent study treatment group and anatomical location. The 95% CIs will be provided for the respective proportions.

Categorical changes from Baseline in overall BMD (defined as lumbar spine and total hip) also will be assessed at 12, 24, 36, and 52 weeks. Femoral neck evaluates a smaller area of bone mass than the total hip and is prone to lower precision in the measurement (Leslie 2007; ISCD Official Positions 2015). Since femoral neck BMD may be associated with discordant readings compared with the total hip or lumbar spine due to technical considerations, it is not expected to add meaningful interpretation of overall BMD changes in response to treatment, though will be included for completeness.

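### LS-mean 95% CIs from models fitted within one group with Baseline as a covariate leave out the sampling variation of Baseline and are too narrow for that group's mean change

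*SAP*

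**What the plan says.** For Baseline-to-Week-52 change endpoints, SAP 7.1.2 plans that "mean change as well as least squares (LS) means change and 95% CI will be summarized". The adjusted part is specified as follows: "LS means and 95% CI will be derived separately for each treatment group using a mixed model repeated measures approach", with the randomization stratification factors as fixed effects. On the remaining terms it says "The Baseline value will be included as a covariate, and an unstructured variance-covariance matrix will be assumed".

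The same structure appears twice more. For uterine and fibroid volume, SAP 7.3.5 uses an ANCOVA with Baseline as a covariate: "This model will be run separately for each treatment group". For bone mineral density, SAP 9.3.4 uses a mixed model that includes the Baseline value, age and BMI: "The model will be generated separately for each parent study treatment group".

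SAP 4.1 sets the level and sidedness: "Confidence intervals, when presented, will generally be constructed at the 95% level" and "All confidence intervals (CIs) will be reported as two-sided unless otherwise stated". The SAP does not say at which Baseline value the LS mean is evaluated, whether its interval is meant to be conditional on the observed baselines, or whether the standard error allows for sampling of Baseline. Only for bone mineral density does it clearly attach an interval to the unadjusted mean: "Percentage changes from baseline along with 95% CIs of mean percentage changes also will be summarized by parent study treatment group and anatomical location".

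**The concern.** Adjusting for Baseline is well suited to a difference between randomized groups, because the sampling error of mean Baseline largely cancels in the difference. SAP section 1 says the methods follow the parent studies, where that applied. Here nothing is differenced: SAP 7.1 rules out treatment comparisons, and each model sees one group only.

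In one group with complete data, the LS mean at the group's own mean Baseline is essentially the raw mean change. Its model standard error, however, reflects only the scatter left after regressing change on Baseline. The uncertainty that comes from having sampled these particular baselines is dropped. An interval labelled 95% for the change from Baseline to Week 52 would then claim more precision than the group's data support. A larger sample does not help, because the ratio of reported to required width does not depend on n.

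**Working it through.** **Inputs from the documents.** Two-sided 95% intervals (SAP 4.1); one model per group with Baseline as covariate (SAP 7.1.2, 7.3.5, 9.3.4).

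**Inputs assumed, because the documents give none.** r is the correlation between Baseline and Week 52 values; k is the Week 52 SD divided by the Baseline SD.

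**The plan's own figure.** Simulated one-group intervals covered the mean change at the observed mean Baseline 94% to 96% of the time. The nominal 95% therefore reproduces for that conditional target.

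**For the group's mean change.**

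- Model SE^2 of the LS mean ≈ s2_res / n.
- Variance of the same estimate over repeated samples = s2_res / n + b^2 Var(Baseline) / n = Var(change) / n, where b is the slope of change on Baseline.
- Reported width / required width = sqrt(1 - R2).
- Coverage = 2 Phi(1.96 sqrt(1 - R2)) - 1.
- With the Baseline SD scaled to 1, b = rk - 1 and Var(change) = 1 + k^2 - 2rk, so R2 = (1 - rk)^2 / (1 + k^2 - 2rk).

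Worked case, k = 1 and r = 0.5: R2 = 0.25 / 1 = 0.25; sqrt(0.75) = 0.866; 1.96 x 0.866 = 1.697; coverage = 91.0%.

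| k | r | R2 | width ratio | coverage |
|---|---|---|---|---|
| 1 | 0.2 | 0.40 | 0.77 | 87% |
| 1 | 0.5 | 0.25 | 0.87 | 91% |
| 1 | 0.8 | 0.10 | 0.95 | 94% |
| 0.75 | 0.2 | 0.57 | 0.65 | 80% |
| 0.75 | 0.5 | 0.48 | 0.72 | 84% |
| 0.75 | 0.8 | 0.44 | 0.75 | 86% |

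**Simulation checks.**

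- One-group ANCOVA, n = 100 and 200, 4,000 runs each: 90.6% to 90.8% at k = 1, r = 0.5, and 81.6% to 82.7% at k = 0.75, r = 0.3. The ordinary t interval for the raw mean change covered 94.4% to 95.5% in every setting.
- Repeated-measures model, four visits, n = 200, 4,000 groups, k = 1: 86.6% at r = 0.2 and 91.2% at r = 0.5.
- Repeated-measures model with random dropout, n = 150, 1,500 runs: about 91.5% at r = 0.5.
- Stratification factors with assumed 75/25 and 65/35 splits and equal LS-mean weights (k = 1): 91.8% at r = 0.5, and 87% rather than about 83% at r = 0. They reduce the shortfall but do not remove it.

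**By endpoint.**

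- *UFS-QoL (absolute change, SAP 7.3.4).* The scales run from 0 to 100, so women with worse baselines have more room to improve. Change is then tied to Baseline, and R2 need not be small.
- *Hemoglobin (SAP 7.3.3).* The change analysis is limited to women at or below 10.5 g/dL at Baseline. That truncates the Baseline range and tends to push k above 1. At an assumed k = 1.5, the same formula gives 92.3% at r = 0.2 and 94.6% at r = 0.5.
- *Percent change (blood loss, volumes, bone mineral density).* Under an assumed multiplicative model, coverage was 94.9% with no relation to Baseline, 94.3% at R2 = 0.06 and 92.1% at R2 = 0.17.

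**The case against.** The strongest reply is that the interval is valid for the mean change at the observed mean Baseline, which is how many analysts read an LS mean. That is correct, and the simulations confirm it. But the SAP never names that target. It sets the LS mean beside the raw mean change as an estimate of the same Baseline-to-Week-52 endpoint, and a reader will take the interval as one for that change.

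A second reply is that little depends on these intervals. SAP 7.1 disclaims inferential statistics. The raw mean is reported with n and SD, so a reader can compute an unadjusted interval. The Bleeding and Pelvic Discomfort and Revised Activities scales also get responder proportions. This stands, and it limits the consequence. It does not justify a 95% label on an interval that falls short for the quantity named.

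A reader might infer that coverage is known to be as low as 80%. The documents do not support this: the figure needs both r = 0.2 and a Week 52 SD 25% below the Baseline SD, and neither document supplies either value. Over a wider grid (k from 0.5 to 1.25, r from 0 to 0.9), coverage runs from about 53% to 95%, so no single band can be claimed.

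**Conclusion.** The defect is in the width of the interval; with complete data the LS mean itself is essentially the raw mean change. As specified, the LS-mean 95% CI is sqrt(1 - R2) times the width of a 95% CI for the group's mean change. The mechanism is certain. The size rests on assumed correlations and SDs: about 87% to 94% coverage for r from 0.2 to 0.8 with equal SDs, and lower if Week 52 values are less spread than Baseline values.

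The concern is mainly the UFS-QoL Symptom Severity, Bleeding and Pelvic Discomfort, and health-related quality-of-life scores. It is probably smaller for hemoglobin, and for percent-change endpoints if these are only weakly related to Baseline.

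A reader might infer that the study's main conclusions are at risk. They are not. The primary responder rate has its own CI for a proportion (SAP 7.2.1). The -2.2% lumbar spine comparison uses the arithmetic mean, with the mixed model as support (Protocol 9.5), and SAP 9.3.4 already plans raw-mean intervals for bone mineral density.

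**What to change.** In SAP 7.1.2, state that the target is the group's mean change and that the standard error of the LS mean includes Baseline sampling variation. Any one of these does it:

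- add b^2 s^2(Baseline) / n to the squared model standard error;
- bootstrap women;
- for absolute change, move Baseline into the response vector as visit 0 and report the Week 52 minus Baseline contrast.

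Apply the same standard-error correction in SAP 7.3.5 and 9.3.4. In 9.3.4, age and BMI need the same treatment if they enter as continuous covariates. Print the ordinary 95% CI beside each raw mean change.

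The first two options keep the planned model, so re-specifying it is not required. No new data are needed, only SAP wording and a few lines of code. The downside is wider intervals, by 1 / sqrt(1 - R2): 1.05 times at R2 = 0.10, 1.15 at 0.25 and 1.29 at 0.40.

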7.2. Primary Efficacy Endpoint

The primary efficacy endpoint of the study is the proportion of women who achieve an MBL volume of < 80 mL AND at least a 50% reduction from parent study Baseline in MBL volume over the last 35 days of treatment as measured by the alkaline hematin method. The primary endpoint will be referred to as responder rate and derived on the basis of the total MBL volume measured at the Week 52/EOT visit window taking into consideration the patient's compliance with return of feminine products and completion of the paper patient Diary (see [Section 7.2.3](#) for details). For the primary analysis, primary endpoint will incorporate the missing data handling rules described in [Section 7.2.4](#).

7.2.1. Primary Efficacy Analysis

The responder rate and two-sided 95% CI will be presented for each treatment group.

7.2.2. Definitions Related to Menstrual Blood Loss

The data sources that will be used to support derivation of responder status include:

- Menstrual blood loss volume determined by the alkaline hematin method;
- Daily patient report of bleeding (yes/no) and use of feminine product (yes/no) captured in the paper patient Diary;
- The status of feminine product (FP) collection return (yes/no) recorded on the electronic case report form (eCRF) page at each visit with specific reasons captured when no product collection was returned.

The total MBL volume is reported from the analysis of FP returned for each collection interval. An inventory of days (with dates) for which FP was collected and returned is also available. This inventory is aligned with patients' reports of bleeding and FP use in the paper patient Diary. The status of FP collection return, and specifically the reason for non-return of FP reported on the Feminine Product Collection eCFR page is used to support derivation of responder status (see [Section 7.2.4](#) for details).

7.2.2.1. Menstrual Blood Loss Volume

All returned feminine products (validated, validated but unauthorized, or unvalidated products) collected at each visit will be analyzed by the alkaline hematin method to obtain the MBL volume. The MBL volume measured over the Week 52/EOT feminine product collection interval (up to 35 days prior to the last dose of treatment) will be used for analysis of the primary efficacy endpoint (see details below). The vendor, KCAS, reports when unauthorized feminine products (products not dispensed for use in the trial) have been returned. KCAS also reports whether the unauthorized products have previously been validated for their analysis. The report details MBL volumes for authorized, unauthorized but validated, and unauthorized and unvalidated products.

7.2.2.2. Baseline Menstrual Blood Loss Volume

Baseline MBL volume is defined as the average MBL volume from the one or two consecutive screening menstrual cycles used to meet the inclusion criteria prior to the date of the first dose of parent study drug as assessed by the alkaline hematin method as follows:

For patients with MBL volume ≥ 160 mL during the screening period, the Baseline MBL volume is the last measurement collected before the first administration of parent study drug.

If the MBL volume is < 160 mL, the Baseline MBL volume is defined as the average of the MBL volume from the two screening menstrual cycles used to meet the inclusion criteria prior to the date of the first dose of parent study drug as assessed by the alkaline hematin method (see Figure 4-2 of the study protocol MVT-601-3001/3002 for details).

7.2.2.3. Week 52/EOT Feminine Product Collection Interval

To ensure collection of all feminine products used during that menstrual cycle, an interval of up to 35 days for measurement of the primary endpoint was selected to accommodate women who continue to have cyclic bleeding on study treatment and whose natural cycle was at the upper end of the normal cycle duration range. This method is consistent with that used during screening for collection of feminine products and with that used for the primary efficacy analysis in the parent studies. Specifically, the feminine product collection interval at Week 52/EOT is driven by types of bleeding patterns experienced by the patients, as described below:

- For patients who continue to have cyclic bleeding, the length of the interval depends on the duration of the patient's natural cycle; this is consistent with the way the Baseline MBL volume was determined (eg, the interval ranging from approximately 21 to 35 days);
- Patients who report irregular, non-cyclic bleeding are instructed to collect and return all feminine product used between study visits, up to 35 days, as per the schedule of events;
- For patients who report amenorrhea on the feminine production collection eCRF page, an interval of last 35 days of treatment will be reviewed to ensure that reported amenorrhea is not due to incomplete collection.

For patients who are in the midst of an episode of cyclic bleeding at the time of the Week 52/EOT visit, the visit window may be extended up to 7 days after the last dose of study drug to ensure patients return all used feminine products over that bleeding episode.

Per protocol, all used feminine products are to be collected at each visit and returned for analysis using the alkaline hematin method. For patients who continue to have menstrual bleeding, study visits are timed such that the feminine products used in the entire menstrual bleeding cycle are collected in one container provided at each visit.

7.2.2.4. MBL Volume at Week 52/EOT

MBL volume at Week 52/EOT is defined as the MBL volume obtained from the feminine product returned over the Week 52/EOT feminine product collection interval, as described above. The MBL volume at Week 52/EOT will be used to derive the primary efficacy endpoint.

If a patient did not return feminine product over the last 35 days of treatment and reported amenorrhea on the feminine product return eCRF page, she will be considered as amenorrhoeic and her MBL volume will be assigned as 0 mL.

